8.3. Guidelines for Follow-up Non-Invasive Testing, Angiography and Reintervention

8.3.1. Follow-up Non-Invasive Testing

The decision whether to perform routine stress testing after ULMCA treatment should depend on the symptomatic state of the subject, as follows:

- The asymptomatic subject. Routine stress testing is strongly discouraged in the asymptomatic subject.
- The subject with atypical symptoms. Routine stress testing may be performed in the subject with atypical symptoms according to the discretion of the treating physicians, or such subjects may be treated conservatively.
- The subject with typical angina or other progressive cardiac symptoms or signs. Subjects with typical cardiac symptoms or evidence of progressive heart disease should in most cases undergo repeat cardiac catheterization; stress testing should not be performed, especially in the subject with possible recurrent disease in the left main stem.

Because of the risk of exercise-induced stent thrombosis, in no case should routine follow-up exercise stress testing be performed within 8 weeks after stent implantation.

Follow-up echocardiography (without exercise) is not mandated by protocol but may be performed at any time during follow-up per the discretion of the treating physicians. Similarly, multislice CT scanning but may be performed at any time during follow-up per the discretion of the treating physicians. However, the use of MSCT in accurately determining in-stent restenosis has not been validated, and thus should in general not be used to guide decision making. MSCT may be useful, however, in determining bypass graft patency.

8.3.2. Follow-up Angiography

Routine follow-up angiography in the asymptomatic subject is not permitted in this study. Prior studies have not demonstrated a benefit of routine follow-up angiography after ULMCA disease, and routine follow-up angiography can result in non clinically indicated revascularization procedures (the "oculostenotic reflex").^{48,49} In the SYNTAX trial, routine follow-up angiography was performed at 15 months in 268 surviving asymptomatic subjects with ULMCA disease randomized to PCI with TAXUS PES vs. CABG. In the PCI group, the mean late loss in the left main stem with PES was only 0.2 mm, and thrombus was present in only 2 subjects (1%). The composite rate of death, MI, stroke or repeat revascularization among PCI subjects undergoing routine angiography was 13% at 15 months (compared to 15.8% in all PCI subjects at 12 months, including those who were symptomatic). Numerous prior studies of drug-eluting stents in subjects with ULMCA disease have demonstrated very low rates (<0.5%) of left main stent thrombosis,^{25, 72, 73} and no prior study of routine angiographic follow-up has been shown to improve outcomes after drug-eluting stents. Routine angiographic follow-up after left main intervention is not recommended by the current ACC/AHA PCI guidelines.²⁷

For subjects who develop atypical chest pain or other symptoms that might reflect ischemia, it is strongly recommended that a nuclear stress test, echocardiographic stress test, or MSCT scan be performed, with subsequent angiography only for positive non-invasive results. Valid indications for follow-up angiography in the present study include any of the following:

- the recurrence of typical angina;
- a positive noninvasive study indicating moderate or severe ischemia, a significant decline in left ventricular function or progressive valve disease;
- progressive heart failure or unstable arrhythmias;
- cardiac arrest;
- or other clinical conditions for which the treating physician believes follow-up angiography is indicated.

The reasons for follow-up angiography will be closely tracked in the case report form.

8.3.3. Repeat Intervention (PCI or CABG)

In subjects who do undergo follow-up angiography, repeat PCI or CABG may only be performed with evidence of ischemia, requiring one of the following to be present:

- \geq 70% diameter stenosis of the treated or new lesions by visual angiographic assessment
- In the case of a visually estimated diameter stenosis of \geq 50% to <70%, either
 - evidence of definite ischemia in the territory of the diseased vessel by prior non-invasive stress testing with imaging evaluation showing ischemia in the questioned myocardial territory, and/or
 - IVUS minimal stent area $\leq 6.0 \text{ mm}^2$ (see IVUS procedure guidelines) for left main lesions or $\leq 4.0 \text{ mm}^2$ for non-left main lesions, and/or
 - intra-procedure FFR ≤ 0.80 (see FFR procedure guidelines).

IVUS is preferred for assessment of left main lesions, and FFR is preferred for assessment of non-left main lesions. In particular, after left main stent implantation, the ostial LCX may often appear significantly or even severely stenosed in the absence of symptoms or ischemia ("pseudo-stenosis"). All subjects with a suspected ostial LCX stenosis, regardless of the degree of angiographic severity (unless occluded), are highly recommended to have demonstrated an FFR ≤ 0.80 in the LCX prior to repeat revascularization, unless there is unequivocal evidence of lateral wall ischemia on non-invasive stress testing.

If repeat revascularization is to be performed, the decision whether to perform PCI or CABG should be made according to the discretion of the treating physicians, ideally by local Heart Team consensus.

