Non-Target Vessel: For the purposes of this trial, the only possible non-target vessel would be the right coronary artery and its major branches that were not treated by either PCI or CABG at the index procedure (unless either the LAD or LCX are occluded at baseline and no attempt was made to revascularize these territories by either PCI or CABG).

Target Vessel Revascularization (TVR): Target vessel revascularization is any repeat percutaneous intervention of the target vessel or bypass surgery of the target vessel

Target Lesion Revascularization (TLR): Target lesion revascularization is defined as any repeat percutaneous intervention of the target lesion or bypass surgery of the target vessel

All revascularization events will be adjudicated as either ischemia-driven or non ischemiadriven

Ischemia-Driven Target Lesion (or Vessel) Revascularization: A target lesion (vessel) revascularization will be considered ischemia-driven if the target lesion diameter stenosis is \geq 50% by QCA (analysis segment measurement, involving the lesion itself and 5 mm of proximal and/or distal margin) and any of the following criteria for ischemia are met:

- A positive functional study corresponding to the area served by the target lesion; or
- Ischemic ECG changes at rest in a distribution consistent with the target vessel; or
- Typical ischemic symptoms referable to the target lesion; or
- IVUS of the target lesion with a minimal lumen area (MLA) of ≤4mm² for non left main lesions or ≤6mm² for left main lesions. If the lesions are *de novo* (i.e. not restenotic), the plaque burden must also be ≥60%; or
- FFR of the target lesion ≤ 0.80
Note: A target lesion revascularization for a diameter stenosis less than 50% might also be considered ischemia-driven by the CEC if there was a markedly positive functional study or ECG changes corresponding to the area served by the target lesion.

Ischemia-Driven Non-Target Vessel Revascularization: A non target vessel revascularization will be considered ischemia-driven if any lesion the non target vessel has a diameter stenosis \geq 50% by QCA with any of the above criteria for ischemia met.

Unplanned revascularization for ischemia: Any repeat revascularization of either a target vessel or non-target vessel with any of the above criteria for ischemia met.

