20.4. Follow-up

Since the site of restenosis after distal ULMCA bifurcation intervention is typically the ostium of the LCX, and since many presumed ostial LCX restenoses are angiographic artifacts (i.e. appear angiographically severe, but in fact are not hemodynamically significant),⁶⁸ it is strongly recommended that FFR be performed before treating any presumed restenotic lesions in the ostial LCX location (regardless of angiographic severity, unless totally occluded) unless there is unequivocal lateral wall ischemia by nuclear or echocardiographic noninvasive testing. If the FFR is >0.80, the ostial LCX lesion should not be treated and, thus, TLR (and possible procedural complications) avoided. For sites that do not use FFR, it is strongly recommended that pre-interventional IVUS of the ostial LCX be performed instead with an MLA >4.0mm² used as the criteria to defer intervention and avoid TLR.¹⁸⁶ Similarly, prior to performing a repeat intervention elsewhere in the coronary tree, if the visually assessed angiographic diameter stenosis is <70%, ischemia should be documented according to either a positive nuclear or echocardiographic noninvasive test in the distribution of the recurrent lesion, or an FFR ≤0.80, or IVUS with a MLA ≤4.0 mm².

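### Section 8.3.3 sets the IVUS criterion for repeat revascularization on minimal stent area, where adjudication and every other significance rule use minimal lumen area

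*Protocol*

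**What the plan says.** Protocol 8.3.3 governs repeat procedures after follow-up angiography: "repeat PCI or CABG may only be performed with evidence of ischemia, requiring one of the following to be present". The first route is at least 70% "diameter stenosis of the treated or new lesions by visual angiographic assessment". For a visual stenosis of 50% to under 70% there are three alternatives:

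- imaging evidence of ischemia in the vessel's territory;
- "IVUS minimal stent area" of at most 6.0 mm² for left main lesions or 4.0 mm² for others;
- FFR of 0.80 or less.

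The IVUS line refers the reader to the IVUS guidelines. The section adds that "IVUS is preferred for assessment of left main lesions".

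Protocol 16.1.4, which defines ischemia-driven revascularization for adjudication, uses the same two cut-offs on a different quantity: "IVUS of the target lesion with a minimal lumen area (MLA". It adds a plaque burden of at least 60% if the lesion is de novo. It also accepts criteria that 8.3.3 does not list, among them "Typical ischemic symptoms referable to the target lesion".

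Protocol 20.4 also works in lumen area. An ostial LCX lesion is deferred above 4.0 mm². "prior to performing a repeat intervention elsewhere in the coronary tree", a lesion under 70% needs a lumen area of at most 4.0 mm² if IVUS is the evidence. No separate left main value is given there.

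**The concern.** Stent area is fixed largely at implantation; lumen area is what remains open. A rule meant to decide whether a follow-up lesion is significant has to use the second. As written, 8.3.3 asks about stent expansion. It cannot register tissue growth inside a well-expanded stent, and it is undefined where there is no stent, which includes the native left main of a subject treated by CABG.

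The wording is a condition on treatment, and Protocol 11.3 allows departures only in medical emergencies. A site treating a left main restenosis on lumen area alone would meet the adjudication standard but depart from 8.3.3. Unplanned revascularization for ischemia is also a component of the second powered secondary endpoint. Adjudication classifies only procedures that were done, while 8.3.3 bears on which are done.

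**Working it through.** **Which quantity each rule uses**

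| Section | Decision | Quantity | Left main | Other |
|---|---|---|---|---|
| 6.5.1 | eligibility | lumen | 6.0 | 4.0 (ostial LAD/LCX) |
| 7.3.2 | index left main PCI | lumen | 6.0 | – |
| 7.5 | ischemia-producing lesion | lumen | – | 4.0, plaque >60% |
| 16.1.4 | adjudication | lumen | 6 | 4 (plaque ≥60% if de novo, either site) |
| 20.1.2 | left main before randomization | lumen | 6.0 | – |
| 20.3.1 | non-left-main PCI | lumen | – | 4, plaque >60% |
| 20.4 | follow-up | lumen | no separate value | 4.0 |
| **8.3.3** | **repeat PCI or CABG** | **stent** | **6.0** | **4.0** |

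Only 8.3.3 differs.

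**Is it loose use of a synonym?** No. The protocol uses stent area elsewhere as its own measure: an expansion target after deployment (above 8.5 mm² in the left main, 20.2; above 5.5 mm² in non-left-main lesions, 20.3.2), and a predictor of events in the IVUS substudy (Appendix C). The 8.3.3 cut-offs match those applied to lumen area elsewhere, which points to a drafting slip.

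**What the literal rule does inside the 50% to under 70% range.** Assume a circular lumen, the stent as reference, and a stent area unchanged since implantation. Lumen area is then stent area × (1 − diameter stenosis)².

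- Left main, stent at 8.5 mm², true 50% stenosis: 8.5 × 0.50² = 2.1 mm². Lumen criterion (≤6.0) met; stent criterion (8.5 against 6.0) not met.
- Other, stent at 5.5 mm², true 50% stenosis: 5.5 × 0.50² = 1.4 mm². Lumen criterion (≤4.0) met; stent criterion (5.5 against 4.0) not met.

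A tighter stenosis lowers the lumen area and leaves the stent area where it was, so the IVUS route stays closed however severe the in-stent narrowing. This applies only to stents that reached the target; IVUS guidance at implantation is recommended, not required.

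**Unstented lesions.** The mention of new lesions stands in the 70% item, not in the item holding the IVUS line, so applying it to IVUS is an inference. It is a reasonable one: the section covers repeat PCI or CABG generally, and nothing limits the 50% to under 70% item to stented segments.

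**The other routes.** All three remain. For suspected left main restenosis they are somewhat weaker than the list suggests: 8.3.1 advises against stress testing in subjects with typical angina or progressive cardiac symptoms, and 20.1.3, on assessment before randomization, warns that left main FFR can mislead when there is downstream disease.

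**Does the cross-reference repair it?** In part. 20.4 shows that lumen area is the quantity, but its only cut-off is 4.0 mm², against 6.0 mm² for the left main in 8.3.3 and 16.1.4.

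**The case against.** The case for leaving it alone is that any site would read lumen. The parent section is headed as guidelines, the line points to IVUS guidance that uses lumen area, and every other significance rule does too. Three alternative routes stay open, and 16.1.4 already adjudicates on lumen area. All of this stands and keeps the point small. It does not make the sentence correct, and 8.3.3 is written as a restriction.

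Three stronger readings are tempting but not supported.

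1. *The distance between expansion targets and cut-offs shows the size of the error.* A target-expanded stent exceeds the 8.3.3 limit by (8.5 − 6.0)/6.0 = 42% in the left main and (5.5 − 4.0)/4.0 = 37.5% elsewhere. On lumen area it would qualify once tissue fills 1 − 6.0/8.5 = 29% or 1 − 4.0/5.5 = 27% of it. These figures ignore the visual gate. In diameter terms the tissue figures are 1 − √(6.0/8.5) = 16% and 1 − √(4.0/5.5) = 15%, far below 50%. They compare thresholds and do not measure impact.
2. *The left main range between 4.0 and 6.0 mm², where 8.3.3 and 20.4 would still differ after a one-word correction, holds many lesions.* 6.5.3 limits the left main reference diameter to 4.25 mm, with post-dilatation to 4.5 mm. A true 50% circular stenosis then leaves at most π/4 × 2.125² = 3.55 mm², or π/4 × 2.25² = 3.98 mm². Both are under 4.0. The range arises mainly for lesions over-called visually or not circular. These do occur, which is one reason to use IVUS.
3. *The second powered secondary endpoint is biased, or one arm is favored.* 8.3.3 could influence which procedures are done, but nothing in the documents gives a count or a direction.

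**Conclusion.** The criterion is wrong as written: 8.3.3 names a quantity that cannot show in-stent narrowing and does not exist for unstented lesions, in conflict with 16.1.4, 20.4 and the eligibility and treatment rules. The finding rests on the text alone. The statement that the IVUS route stays closed also assumes a stent at its expansion target whose area has not changed.

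Its practical effect is limited. It concerns lesions of 50% to under 70% that meet neither the imaging nor the FFR criterion, at sites that apply the sentence literally. Event classification follows 16.1.4, and the primary endpoint definition (death, MI, stroke) is unaffected. How many subjects are affected, and in which arm, cannot be derived. It merits correction as an inconsistency in a treatment rule; it does not threaten the trial's conclusions.

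**What to change.** - **8.3.3:** replace stent area with lumen area, keeping ≤6.0 mm² for left main and ≤4.0 mm² for other lesions.
- **8.3.3:** add the 16.1.4 condition of plaque burden ≥60% for de novo (non-restenotic) lesions. Without it, a new lesion could be treated on lumen area alone and then fail the IVUS criterion at adjudication.
- **8.3.3:** state that the ostial LCX uses 4.0 mm². This is needed because 16.1.4 counts the first 5 mm of the LAD and LCX as part of the left main target lesion.
- **20.4:** add ≤6.0 mm² for left main lesions; keep 4.0 mm² for the ostial LCX and other non-left-main lesions.

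Cost: a minor wording amendment, site notification, and IRB/EC acknowledgment or approval in writing before implementation (11.2.1), across about 165 centers. It can be folded into the next amendment. No new data, tests or patients are needed. The downside is that a few more repeat procedures may be permitted.

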8.4. Adverse Events

An adverse event (AE) is any untoward medical occurrence, unintended disease or injury, or untoward clinical signs (including abnormal laboratory findings) in subjects, users or other persons, whether or not related to the investigational medical device.

NOTE 1: This definition includes events related to the investigational medical device or the comparator.

NOTE 2: This definition includes events related to the procedures involved.

NOTE 3: For users or other persons, this definition is restricted to events related to investigational medical devices.

An AE can therefore be any unfavorable and unintended sign (including an abnormal laboratory finding), symptom, or disease temporally associated with the use of a medicinal (investigational) product, whether or not related to the medicinal (investigational) product.

Stable, chronic, pre-existing conditions are not to be reported as AEs. However, worsening of a pre-existing condition that occurs after a subject's participation in the trial is considered an AE and must be reported as such.

Planned procedures (scheduled prior to the index procedure) that occur after the index procedure are not considered AEs and are not to be reported as such. Complications from such procedures, however, are considered AEs and must be reported.

Non-cardiac related abnormal laboratory values will not be considered AEs unless:

• the investigator determined that the value is clinically significant,

- the abnormal lab value required intervention, or
- the abnormal lab value required subject termination from the study.

The investigator should report the event(s) to the IRB/EC according to the institution's reporting requirements.

Adverse Event Reporting

The Investigator will monitor the occurrence of adverse events for each subject during the course of the study. For the purpose of this protocol, the reporting of adverse events begins directly after randomization. All adverse events (AEs) reported by the subject, observed by the Investigator, or documented in medical records will be listed on the Adverse Event Case Report Forms.

Adverse events will be monitored throughout the course of the

study. Serious Adverse Events

If the adverse event meets any of the criteria below, it is regarded as a serious adverse event (SAE):

a) Led to a death,

b) Led to a serious deterioration in health that either:

1) Resulted in a life-threatening illness or injury, or

2) Resulted in a permanent impairment of a body structure or a body function, or

3) Required in-patient hospitalization or prolongation of existing hospitalization, or

4) Resulted in medical or surgical intervention to prevent life threatening illness or injury or

permanent impairment to a body structure or a body function.

c) Led to fetal distress, fetal death or a congenital abnormality or birth defect.

d) An important medical event that may not result in death, be life-threatening, or require hospitalization but may be considered serious when, based upon appropriate medical judgment, may jeopardize the patient or subject and/or may require intervention to prevent one of the outcomes listed in this definition.

NOTE 1: This includes device deficiencies that might have led to a serious adverse event if a) suitable action had not been taken or b) intervention had not been made or c) if circumstances had been less fortunate. These are handled under the SAE reporting system. NOTE 2: A planned hospitalization for pre-existing condition, or a procedure required by the Clinical Investigation Plan, without a serious deterioration in health, is not considered to be a serious adverse event.

The investigator will report serious adverse events to the IRB/EC according to the institution's reporting requirements.

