4. STUDY DESIGN

4.1. Study Design

A total of approximately 2900 subjects will be targeted in the study.

The prospective, unblinded, randomized multicenter trial will randomize about 1900 subjects at approximately 165 U.S. and international centers. Following diagnostic angiography demonstrating significant ULMCA disease and the consensus of the local Heart Team (qualified participating interventional cardiologist and cardiac surgeon) that the subject meets all the study entry criteria, subjects will be consented and randomized 1:1 to: a) PCI using the XIENCE stent, or b) CABG. Follow-up for all randomized subjects will continue for 5 years with a potential for additional follow-up to 10 years.

An additional group of approximately 1000 subjects who are not eligible for randomization or for other reasons are not randomized will be consented for the Universal Registry. All patients with left main disease without prior CABG in whom the visual estimated diameter stenosis is greater than or equal to 50% will be eligible for the EXCEL registry. These subjects will be consented for the Universal Registry, and followed through the time of initial treatment as per

standard of care with either PCI, CABG or medical therapy. No adverse event data will be collected for Universal Registry subjects.

Approximately 100 consecutive subjects from the Universal Registry with a \geq 50% and <70% visually estimated angiographic diameter stenosis who otherwise meet all enrolment criteria, but without significant ischemia by noninvasive testing consistent with significant ULMCA disease, and in whom IVUS shows a MLA >6.0 mm² and/or a FFR >0.80 will be analyzed separately as intermediate lesion subjects, and followed through the time of initial treatment as per standard of care with either PCI, CABG or medical therapy.

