6.6. Subject Flow

Every subject who presents with ULMCA or left main equivalent disease to any qualified interventional cardiologist or cardiac surgeon participating in this trial will be evaluated by the local Heart Team including detailed assessment of the inclusion and exclusion criteria, the

SYNTAX score calculated from diagnostic angiogram, history, physical examination and laboratory evaluations. If the information is not adequate for the local Heart Team to make their decision, then further testing and/or an angiogram will be performed after informed consent is obtained from the subject.

The Study Coordinators should facilitate the local team conference. Each site will take minutes of each conference for the investigators sites. The members will review the collected baseline information e.g. the angiogram (including the SYNTAX score), and demographic characteristics. During the local Heart Team conference, the members will jointly decide whether the subject is eligible for randomization or for the Universal Registry.

If both members of the local Heart Team determine that the subject meets the eligibility criteria of the Randomized Study, the subject will be deemed meeting randomization criteria and enters the "Randomized Clinical Trial" (Figure 6.1).

• Note: If all the eligibility criteria are met *except* that the diagnostic angiography demonstrates a ULMCA lesion or left main equivalent lesion(s) which either the interventional cardiologist and/or cardiac surgeon of the local Heart Team believes is ≥50% but <70% in diameter stenosis by visual estimate, the subject is not yet eligible for randomization without further evaluation. If non-invasive evidence of ischemia referable to a hemodynamically significant ULMCA lesion as defined in Section 6.5.1 is not present, the subject must have IVUS (preferably) or FFR assessment of the ULMCA lesion. In this case, the subject will be consented for randomization prior to the invasive IVUS/FFR procedure. If the IVUS/FFR procedure demonstrates that the ULMCA lesion is significant, the subject may be randomized at that point in the catheterization laboratory, and PCI performed if the randomization is to PCI. If the randomization is to CABG, the catheterization laboratory procedure is terminated and CABG performed as per standard of care.

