7.2.8. IVUS / FFR

Prior to randomization, all subjects with an angiographically intermediate left main lesion (\geq 50 - <70 DS% by consensus visual assessment by the Heart Team) without noninvasive evidence of a hemodynamically significant left main lesions must undergo additional invasive investigation after informed consent such as IVUS (preferred) or FFR to document lesion severity. If these tests provide data that the patient meets the inclusion criteria, the subject may be randomized; if not, the subject should be included in the Universal Registry. (Refer to Section 18, Appendix C.)

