8.2. Clinical Follow-up

Subjects will have clinical follow-up as a telephone contact or office visit, at the time points listed below. Day 0 is the date of the randomization assignment which can be on the same date or earlier than the date of the randomized procedure. All adverse events (AE) will be recorded from Day 0. Patient follow-up will occur from the day of randomized procedure as shown below. Office visits are strongly recommended for the annual clinical follow-up. If that is not possible, phone contact with subject or subject's local physician is acceptable. As a last resort, notification of death by civil registry will be accepted.

- 30 ± 7 days (office visit preferred)
- 6 months \pm 14 days (telephone contact or office visit)
- Visits at 1, 2, 3, 4, and 5 years with windows of -30 days, +60 days (office visit preferred)
- Potential visits:
 - Yearly visits at 6, 7, 8, 9, and 10 years with window of-30 days, +60 days (office visit preferred)

All efforts must be made to obtain follow-up information on subjects who have visited a clinic or hospital, underwent procedures or have been treated for adverse events in a non-study-related hospital(s). Non study hospital related material will be collected and reviewed at the study coordinating centers. All follow-up angiograms must be collected (whether at the study hospital or an outside hospital) and sent to the angiographic core laboratory for independent analysis.

The following data will be collected at 30 days, 6 mo, 1 year, 2 years, 3 years, 4 years and 5 years follow-up time points (and potential 6-10 year visits).

• Data regarding adverse events (with related laboratory tests results), including but not limited to death, MI, stroke, TIA, bleeding, renal insufficiency, repeat revascularization procedures, repeat hospitalization for any reason, ECGs, details of any subsequent repeat coronary angiography and results of such, if applicable.

- Details of any subsequent coronary interventions (for example, repeat PCI or CABG). The physician must record in the source documents whether a revascularization was carried out during the period between the index procedure and the follow-up visit. The physician must then document whether the revascularization was based on clinical signs and symptoms and available ancillary data and whether the procedure was ischemia driven according to the definition specified in this protocol (Refer to Section 16, Appendix A).

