Iterative IVUS and post-dilation should be performed until the ULMCA minimum stent area is >8.5mm² and the ostial/proximal LAD minimum stent area is at least >5.5mm² and preferably matched to the distal reference vessel diameter if larger. Observational data in non-LMCA lesions has shown that in general the larger the minimal stent area the lower the likelihood of restenosis and stent thrombosis^{183, 184, 185} and thus post-dilation with non compliant balloons sized up to 0.25-0.5mm less than the IVUS determined true vessel diameter (average media-media dimension) to safely achieve the largest maximal luminal dimension is recommended. It is strongly recommended that IVUS is also performed post-LMCA stenting from at least one epicardial coronary artery, usually the LAD, with pullback into the aorta (disengaging the guide to ensure the ostium is not missed). If a 1-stent technique is used (most commonly from the ULMCA into the LAD, "crossing over" the LCX), it is desirable but not mandatory that the ostial LCX also be imaged post-intervention if possible. If a 2-stent technique is used, IVUS pullback across the LAD and LCX is strongly recommended if the IVUS catheter passes easily into the LCX. LCX or side branch imaging should not be pursued aggressively to avoid IVUSrelated (or pressure wire-related) complications. If the IVUS catheter or pressure wire can be safely positioned into the LCX, then, in general, an LCX ostium lumen area >4.0mm² (single stent strategy) or >5.5mm² (two stent strategy) or an FFR >0.80 (single stent strategy) indicates that no further intervention is necessary.

Severe dissections present by IVUS (residual true lumen within the dissection flap $\leq 8.5 \text{mm}^2$ in the ULMCA either proximal or distal to the stent or $\leq 5.5 \text{mm}^2$ in the proximal LAD or LCX distal to the stent) should in general receive an additional stent. Malapposition with stent area $\leq 8.5 \text{mm}^2$ in the ULMCA or $\leq 5.5 \text{mm}^2$ in the proximal LAD or LCX should in general be treated by additional post-dilatation with larger balloons.

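### AE reporting starts at randomization, so serious harm from the protocol-required IVUS/FFR done after trial consent is not collected in subjects who are then not randomized

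*Protocol*

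**What the plan says.** **Reporting window.** Protocol 8.4 says that "the reporting of adverse events begins directly after randomization". Protocol 8.2 says "All adverse events (AE) will be recorded from Day 0" and that "Day 0 is the date of the randomization assignment".

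**Invasive step before randomization.** Under Protocol 7.2.8, subjects with an intermediate left main lesion and no non-invasive evidence of significance "must undergo additional invasive investigation after informed consent such as IVUS (preferred) or FFR to document lesion severity". Protocol 6.6 fixes the order: "the subject will be consented for randomization prior to the invasive IVUS/FFR procedure". Sections 6.6 and 20.1.3 allow randomization in the catheterization laboratory once the test is positive. Section 6.6 also allows other testing or an angiogram after consent when the Heart Team lacks the information to decide.

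**After a negative test.** Section 7.2.8 sends the subject to the Universal Registry. Protocol 4.1 says of that registry: "No adverse event data will be collected for Universal Registry subjects". The registry schedule in 7.1 has no safety row.

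**Analysis.** Protocol 9.1.5 and SAP 2.4 and 4.4 summarize adverse events for the ITT population only, that is, for randomized subjects.

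**The concern.** Between trial consent and randomization, some subjects have an invasive coronary procedure because the protocol requires it to settle eligibility. During that interval the AE window, as 8.2 and 8.4 are worded, is not open. For a subject who is never randomized it does not open later either.

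The selection is unfavorable. Under 20.1.2 a second IVUS pullback is needed in practice only when the first shows an MLA above 6.0 mm², so subjects heading for a non-significant result may have more instrumentation before they enter a registry without AE collection. A complication can also block randomization: 6.5.2, for example, excludes a subject whose CK-MB is above the local upper limit of normal. The more serious the event, the less likely it is to leave a trial record.

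At stake is the completeness of safety information on a procedure that the trial requires of people who have consented to it. The comparison of PCI with CABG is not at stake.

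**Working it through.** No figure in the plan bears on this and no arithmetic applies. The check is to follow a consented intermediate-lesion subject along each route and ask whether any text opens an AE window.

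1. **Consent to test.** The subject signs the randomized-trial consent (6.6) and then has the required IVUS or FFR (7.2.8, 20.1.1). No text in 6.4, 6.6, 7.2.8, 8.2, 8.4 or Appendix E starts AE or SAE reporting at consent or at the start of this procedure.

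2. **Route A: test negative, not randomized.** The subject goes to the registry (7.2.8), where 4.1 rules out AE data. A dissection or access bleed during the test is not collected. The plan text leaves no room for another reading.

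3. **Route B: a complication prevents randomization.** There is no randomization date, so neither 8.2 nor 8.4 ever applies. Section 6.2 asks subjects who are not randomized to consent to the registry, and 4.1 again rules out AE data. The result is as in Route A.

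4. **Route C: test positive, then randomized.** Three places give different answers for an event during the test:
   - 8.4, read literally, excludes an event that occurred before the randomization call.
   - 8.2 counts from a date. An event on the day of on-table randomization could count as Day 0. If randomization follows on a later date, it does not.
   - In the 7.1 schedule the (S)AE reporting bar appears to begin in the pre-procedure/baseline column, which also holds consent, IVUS/FFR and treatment assignment. The table layout as available is not reliable enough to be sure.

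   Harm that first appears or worsens after randomization is reportable on any reading. Capture on Route C is therefore unclear rather than absent.

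5. **How many.** Protocol 4.1 plans about 100 intermediate-lesion registry subjects, defined by their IVUS or FFR result and not by when they were imaged. Section 20.1.3 provides for intermediate-lesion subjects who had not consented before catheterization, so some may have been imaged outside the trial. About 100 is thus an upper bound on Route A within that group. Route B subjects need not meet the group's definition, and the documents give no count for them. They also give no complication rate, so no expected number of lost events can be derived.

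**The case against.** The strongest defense is that starting AE collection at randomization is a coherent choice. Safety is compared between randomized arms in the ITT population, and events before allocation cannot inform that comparison. Institutional IRB/EC reporting (8.4, 8.4.1) continues regardless, and DSMB procedures are in a separate charter (8.5) that is not available here. The first part stands: the randomized comparison is unaffected. IRB/EC reporting, however, does not bring the event into the trial's safety data, and a charter can show the DSMB only what is collected.

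A reader might also infer more than the documents support:

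- **That harm from this step is always lost.** It is not, because some events in randomized subjects are or may be captured (Route C).
- **That the reporting window contradicts the AE definition.** Section 8.4 notes that "This definition includes events related to the procedures involved". That sentence says what counts as an adverse event. The later sentence says when reporting begins. The two are compatible, although the definition shows that these events would qualify if the window were open.
- **That Section 20.2 acknowledges complications of this test.** Its remark on IVUS and pressure-wire complications concerns circumflex or side-branch imaging around left main stenting, not the diagnostic study in 20.1.
- **That subjects with a negative test bear risk without benefit, or are not followed.** Sections 20.1.2 and 20.1.3 use a negative result to defer left main revascularization, and 20.1.3 describes deferral after a negative FFR as safe. Registry subjects are followed through initial treatment (4.1), though without AE data.
- **That a specific number of serious events goes unreported.** Any such count would need a complication rate and a number imaged, and the documents supply neither.

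**Conclusion.** The gap is real but narrow. If the plan is followed as written, serious complications of a protocol-required IVUS or FFR, performed after randomized-trial consent, are not collected in subjects who are then not randomized. For those who are randomized, the status of an event shortly before on-table randomization is ambiguous, and 7.1, 8.2 and 8.4 need to be reconciled.

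The size is unknown. About 100 subjects is a ceiling for the intermediate-lesion registry group, resting on the planned number in 4.1 and on the assumption that all were imaged after trial consent, which 20.1.3 shows need not be so. The finding itself depends on no assumed rate. It affects safety ascertainment only: the primary and powered secondary endpoints are counted from randomization, so their estimates, alpha and power do not change. The change is worth making because it closes a participant-safety gap at very little cost.

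**What to change.** - **Protocol 8.2 and 8.4:** start SAE and procedure-related AE reporting at signature of the randomized-trial consent for any subject having protocol-required IVUS, FFR or angiography before randomization. Continue through discharge from that procedure, whether or not the subject is randomized.
- **Protocol 4.1:** make this the one stated exception to the rule that registry subjects contribute no AE data.
- **Protocol 7.1:** align the start of the (S)AE reporting bar with the revised 8.2 and 8.4.
- **DSMB reporting:** present these events in a separate pre-randomization listing, outside the ITT safety tables.
- **Unchanged:** Day 0 remains the randomization date for all efficacy endpoints.

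The existing SAE form and the three-calendar-day limit in 8.4.1 can be used as they stand. The cost is a wording amendment and a few extra SAE reports from subjects outside the ITT set.
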